12.2.1.2 Serious Adverse Events

For more detailed instructions on SAE reporting, refer to the Serious Adverse Event Form Completion Guidelines contained in Section 5 of the ISF.

AEs defined as serious and which require reporting as an SAE (excluding events detailed in Section 12.1.2.1 and 12.1.2.2 above) should be reported on an SAE Form. When completing the form, the Investigator will be asked to define the causality and the severity of the AE, which should be documented using the CTCAE version 4.0.

On becoming aware that a patient has experienced an SAE, the Principal Investigator (or delegate) must complete, date and sign an SAE Form. The form should be faxed together with a SAE Fax Cover Sheet to the Trial Office using one of the numbers listed below, as soon as possible and no later than 24 hours after first becoming aware of the event:

To report an SAE, fax the SAE Form with an SAE Fax Cover Sheet to:

图 [name] or 图 [name]

On receipt, the Trial Office will allocate each SAE a unique reference number. This number will be transcribed onto the SAE Fax Cover Sheet by the Trial Office, which will then be faxed back to the site as proof of receipt. If confirmation of receipt is not received within 1 working day, please contact the Trial Office. The SAE reference number should be quoted on all correspondence and follow-up reports regarding the SAE. The SAE Fax Cover Sheet completed by the Trial Office should be filed with the SAE Form in the ISF.

For SAE Forms completed by someone other than the Investigator, the Investigator will be required to countersign the original SAE Form to confirm agreement with the causality and severity assessments. The form should then be returned to the Trial Office in the post and a copy kept in the ISF.

Investigators should also report SAEs to their own Trust in accordance with local practice.

12.2.1.3 Provision of follow-up information

Patients should be followed up until resolution or stabilisation of the event. Follow-up information should be provided on a new SAE Form (refer to the SAE Form Completion Guidelines for further information).

12.2.2 Trial Office

On receipt of an SAE Form, relatedness will be determined independently by a Clinical Coordinator. The Clinical Coordinator will also assess all related SAEs for expectedness. If the event is unexpected (i.e. is not defined in the protocol as an expected event) it will be classified as an Unexpected and Related SAE.

12.2.3 Reporting to the Research Ethics Committee

12.2.3.1 Unexpected and Related Serious Adverse Events

The Trial Office will report all events categorised as Unexpected and Related SAEs to the Research Ethics Committee (REC) within 15 days.

Page **30** of **48** Version 4.0, 15th March 2016

12.2.3.2 Other safety issues identified during the course of the trial

The REC will be notified immediately if a significant safety issue is identified during the course of the trial.

12.2.4 Investigators

Details of all Unexpected and Related SAEs and any other safety issue which arises during the course of the trial will be reported to Principal Investigators. A copy of any such correspondence should be filed in the ISF.

12.2.5 Data Monitoring Committee

The independent Data Monitoring Committee (DMC) will review all SAEs.

Page **31** of **48** Version 4.0, 15th March 2016

13 DATA HANDLING AND RECORD KEEPING

13.1 Data Collection

The Case Report Form (CRF) will comprise the following forms:

Form	Summary of data recorded	Schedule for submission		
Eligibility Checklist	Confirmation of eligibility	As soon as possible after registration		
Registration	Patient details; confirmation of local diagnosis of non-high grade DCIS	As soon as possible after registration		
Randomisation	Patient contact details; details of stratification variables; intended surgery	As soon as possible after randomisation		
Baseline	Details of biopsy histology (with copy of diagnostic biopsy report), concomitant medications (HRT, endocrine therapy (current/planned), NSAIDs)	Within 1 month of randomisation		
Surgery	Details of type of surgery performed, pathology of the DCIS specimen and any invasive disease identified, adverse events	Thirty days following completion of planned surgery (ies)		
Additional Treatment	Details of any radiotherapy, endocrine therapy, chemotherapy administered and adverse events	As soon as possible following any additional treatment performed or commenced		
Additional Investigations	Details of any additional mammography, other imaging or other biopsies performed	As soon as possible following any additional imaging or biopsies.		
Annual Follow-up	Survival, outcome of annual mammogram and record of related interventions and referrals, concomitant medications (HRT, endocrine therapy, NSAIDs), persisting protocol related adverse effects, health resource usage	Within 1 month of patient annual mammogram or as soon as possible following investigations or treatment if indicated		
Withdrawal	Date of withdrawal, type of withdrawal	Immediately following patient's request		
Subsequent DCIS Report	Date subsequent DCIS confirmed, side and site of cancer, diagnostic method	As soon as possible following confirmation of subsequent DCIS		
Invasive Breast Cancer	Date invasive breast cancer confirmed, side and site of cancer, method of detection	As soon as possible following confirmation of invasive breast cancer		
New (or non-breast cancer) or Metastatic Cancer	Date cancer confirmed, side and site of cancer, method of detection, details of biopsy (if applicable) and treatment details	As soon as possible following confirmation of new or metastatic cancer		
Deviation	Date of deviation, type of deviation	Immediately upon discovering deviation		
Death	Date of death, details of death	Immediately upon notification of patient's death		

The CRF must be completed, signed and dated and returned to the Trial Office by the Investigator or an authorised member of the site research team (as delegated on the SS&DL) within the timeframe listed above. Entries on the CRF should be made in ballpoint pen, in blue or black ink, and must be legible. Any errors should be crossed out with a single stroke, the correction inserted and the change initialled and dated. If it is not obvious why a change has been made, an explanation should be written next to the change.

Page 32 of 48 Version 4.0, 15th March 2016

Data reported on each form should be consistent with the source data. The exception to this would be QoL data and health economics data which will be recorded directly onto CRF and is therefore considered source data. Any discrepancies between the CRF and source data should be explained. If any information is not known, this must be clearly indicated on the form. All missing and ambiguous data will be queried. All sections are to be completed before returning.

In all cases it remains the responsibility of the Investigator to ensure that the CRF has been completed correctly and that the data are accurate.

The completed originals should be sent to the Trial Office and a copy filed in the ISF.

Trial forms may be amended by the Trial Office, as appropriate, throughout the duration of the trial. Whilst this will not constitute a protocol amendment, new versions of the form must be implemented by participating sites immediately on receipt.

13.2 Archiving

It is the responsibility of the Principal Investigator to ensure all essential trial documentation and source records (e.g. signed Informed Consent Forms, Investigator Site Files, Pharmacy Files, patients' hospital notes, copies of CRFs etc.) at their site are securely retained for at least 10 years after the end of the trial or following the processing of all biological material collected for research, whichever is the later. Do not destroy any documents without prior approval from the CRCTU Document Storage Manager.

14 QUALITY MANAGEMENT

The trial is being conducted under the auspices of the CRCTU according to the current guidelines for GCP. Participating sites will be monitored by CRCTU staff to confirm compliance with the protocol and the protection of patients' rights as detailed in the Declaration of Helsinki 1996 (Appendix 3).

14.1 Site Set-up and Initiation

All sites will be required to sign a Clinical Study Site Agreement prior to participation. In addition, all participating Investigators will be asked to sign the necessary agreements and registration forms and supply a current CV to the Trial Office. All members of the site research team will also be required to sign the SS&DL which should be returned to the Trial Office. Prior to commencing recruitment all sites will undergo a process of initiation. Key members of the site research team will be required to attend either a meeting or a teleconference covering aspects of the trial design, protocol procedures, AE reporting, collection and reporting of data and record keeping. Sites will be provided with an ISF containing essential documentation, instructions, and other documentation required for the conduct of the trial. The Trial Office must be informed immediately of any change in the site research team.

14.2 On-site Monitoring

Monitoring will be carried out as required following a risk assessment and as documented in the LORIS Trial Quality Management Plan. Additional on-site monitoring visits may be triggered, for example, by poor CRF return, poor data quality, low SAE reporting rates, or an excessive number of patient withdrawals or deviations. If a monitoring visit is required, the Trial Office will contact the site to arrange a date for the proposed visit and will provide the site with written confirmation. Investigators will allow the LORIS Trial staff access to source documents as requested.

14.3 Central Monitoring

Where a patient has given explicit consent sites are requested to send in copies of signed Informed Consent Forms C for in-house review.

Trials staff will be in regular contact with the site research team to check on progress and address any queries that they may have. Trials staff will check incoming CRFs for compliance with the protocol, data consistency, missing data and timing. Sites will be sent Data Clarification Forms requesting missing data or clarification of inconsistencies or discrepancies.

Sites may be suspended from further recruitment in the event of serious and persistent non-compliance with the protocol and/or GCP, and/or poor recruitment. Any major problems identified during monitoring may be reported to the TMG and the relevant regulatory bodies. This includes reporting serious breaches of GCP and/or the trial protocol to the REC.

Page **33** of **48** Version 4.0, 15th March 2016

14.4 Audit and Inspection

The Investigator will permit trial-related monitoring, audits, ethical review, and regulatory inspection(s) at their site, providing direct access to source data/documents.

Sites are also requested to notify the Trial Office of any inspections.

14.5 Notification of Serious Breaches

Sites are requested to notify the Trial Office of a suspected trial-related serious breach of GCP and/or the trial protocol. Where the Trial Office is investigating whether or not a serious breach has occurred, sites are also requested to cooperate with the Trial Office in providing sufficient information to report the breach where required and in undertaking any corrective and/or preventive action.

The conditions and principles of GCP in connection with that trial or;

The protocol relating to that trial, within 7 days of becoming aware of that breach

For the purposes of this regulation, a "serious breach" is a breach which is likely to effect to a significant degree:

The safety or physical or mental integrity of the subjects of the trial; or

The scientific value of the trial

15 END OF TRIAL DEFINITION

For the purposes of REC approval, the end of trial date is deemed to be 6 months after the date of last data capture or the final analysis of predictive biomarkers, whichever is later. This will allow sufficient time for the completion of protocol procedures, data collection and data input.

The duration of time for which patient follow-up data will be collected is dependent on future funding arrangements. Current funding is secured for this to continue for 10 years after the start of the trial, and further funding will be sought for this to continue long term.

The LORIS Trial Office will notify the REC that the trial has ended and a summary of the clinical trial report will be submitted to the REC within 12 months of the end of trial.

16 STATISTICAL CONSIDERATIONS

The first part of the trial is a Feasibility Study, the aim of which is to demonstrate enough eligible patients can be identified and recruited over the course of the trial to robustly answer the main trial objectives. The patients randomised during the two-year Feasibility Study will form part of the total (932) patients to be recruited.

The success of the Feasibility Study will be determined by showing a sufficient number of patients can be randomised meeting a combination of outcomes that ensures the main trial can adequately recruit to target within the given timeframe.

16.1 Feasibility Study

16.1.1 Definition of Outcome Measures

See Section 2.1.2 Outcome Measures.

16.1.2 Analysis of Outcome Measures

The only objective of the Feasibility Study is to show that the number of patients identified to take part in the study that are subsequently shown to be eligible, are consented and then randomised is sufficient to enable the main trial to continue and recruit an adequate number in a timely manner to robustly answer the main trial objective. No formal statistical testing will take place during the feasibility phase. Descriptive statistics as outlined in Sections 16.1.3 and 16.1.4 will be calculated in order to monitor and determine if progression to the main trial is feasible. The specific progression criteria are detailed below in Section 16.1.5

16.1.3 Planned Interim Analyses

Assessment of the success of the feasibility phase will be made at the end of the second year of recruitment. This approach recognises that there is likely to be a learning curve for both individual sites and the trial as a whole and allows time for specific recruitment problems to be identified and addressed. The Trial Coordinator will maintain close contact with sites and gather feedback from sites regarding both problems and successes in relation to performance on the above outcome measures. The TMG will hold monthly teleconferences during the feasibility phase of the study to review the screening log information and completed Accept/Decline Questionnaires to determine what actions are required to address any recruitment issues. The DMC will convene after 12 months of opening to review the feasibility outcome measures at the half way stage.

16.1.4 Planned Final Analysis

Assessment of the progression criteria will take place at the end of the twenty-fourth month of the Feasibility Study. Success in the progression criteria would demonstrate how the main trial can achieve the targeted recruitment and robustly answer the main trial objectives as detailed below. If the progression criteria are met, the trial will proceed, and will initiate at least 60 sites and will recruit for an additional 4 years to achieve the target of 932 patients.

16.1.5 Specific Progression Criteria from Feasibility Study to Main Trial

- 20 sites trained, open and recruiting by the end of year 2
- 60 patients randomised by the end of year 2
- · Mean monthly recruitment of at least 6 patients in the last 4 months, as defined above

16.2 Main Trial

16.2.1 Definition of Outcome Measures

See Section 2.2.2 Outcome Measure of Main Trial.

16.2.2 Analysis of Outcome Measures

The primary research question to be addressed by this analysis asks if active monitoring for newly diagnosed, asymptomatic, low grade DCIS is non-inferior in terms of ipsilateral invasive breast cancer survival time when compared to surgical intervention to remove all traces of DCIS at diagnosis.

The primary aim is to test the null hypothesis that active monitoring of women diagnosed with low risk DCIS is not non-inferior in terms of invasive breast cancer free survival time compared to treatment with surgery. Invasive breast cancer survival time will be compared across the two arms on a per protocol and intent-to-treat basis, using a 1-sided (5% significance level) log-rank test for non-inferiority and a hazard ratio with a one-sided 95% confidence interval.

There is very little relevant evidence of the actual ipsilateral invasive breast cancer rate amongst low risk DCIS patients and an event rate of 2.5% at 5 years reflects current evidence (26). A difference in invasive breast cancer survival of no more than 2.5% is judged as clinically acceptable both by the TMG and the wider breast cancer clinical community. This gives a non-inferiority margin for the trial defined as an absolute reduction in the 5 year ipsilateral invasive breast cancer free survival rate at 5 years of 2.5% i.e. from 97.5% to 95% and this equates to a hazard ratio of HR=2.02 . Models for survival data will be considered to take into account the stratification factors and other potentially important prognostic factors.

All analyses will be carried out for both per protocol and intent to treat study populations. The primary and secondary outcomes will be calculated for all patients and compared between treatment groups. Time to event outcomes will be calculated for all patients and methods described by Kaplan and Meier used to present survival curves. The log-rank statistic will be used to test hypotheses.

Results from the Brief COPE will allow us to dichotomise women into two groups, those who manage a situation using a problem focused approach and those who have a detached method of coping.

The STAI permits us to measure changes in state anxiety over time. We will examine changes using Analysis of Covariance (ANCOVA) with baseline trait and state anxiety as covariates.

Page **35** of **48** Version 4.0, 15th March 2016

The SF-36v2 measures overall health related QoL by examining changes in the 8 health domains (physical functioning, role-physical, bodily pain, general health, vitality, social functioning, role-emotional and mental health) from baseline over time. Data will show how QoL is affected within and between the two groups (Surgery and Active Monitoring) over a 5 year period.

Health economic data will be used to provide a cost-effectiveness and cost-utility analysis and sensitivity analysis will be performed. The first stage of the economic analysis will be conducted at the end of the Feasibility Study. A second and final stage of analysis will be undertaken towards the end of the trial, using the data analyses from the trial, when 75% of the patients have reached 5 years follow-up. At the last stage there will be two components to the analysis: a within trial analysis and a model-based analysis. The evaluation of the Feasibility Study (after 2 years) will be a model based analysis only. The purpose of this is to ensure all relevant data for conducting the full economic evaluation are being appropriately identified and collected.

Model-based analysis will be carried out at the end of the Feasibility Study and again when 75% of patients have reached 5 years follow-up.

A decision analytic model will be used to allow the extrapolation of cost and effectiveness parameters beyond the data observed in a clinical trial (and to allow extrapolation to other settings). The model will, therefore, consider treatment over total disease duration and will include surgical treatments provided in the longer term. An individual sampling model (such as a Markov model) or similar model will be used to ensure time to event can be analysed. The model-based analysis will initially be conducted at Stage 1 and draw upon follow-up data up to 24 months (feasibility phase) and also make use of published data and assumptions to predict costs and benefits into the long-term. The analysis will then be repeated at Stage 2, using the longer follow-up data, but still predicting costs and effects beyond the trial end.

Results of all economic analyses will be presented using cost-effectiveness acceptability curves to reflect sampling variation and uncertainties in the appropriate threshold cost-effectiveness value. We shall also use simple and probabilistic sensitivity analyses to explore the robustness of these results to plausible variations in key assumptions and variations in the analytical methods used, and to consider the broader issue of the generalizability of the results.

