The radiological, pathological and translational data from this trial will enable better future selection of those patients who can safely avoid surgery.

Women will be able to make appropriate choices based on the chances of invasive disease developing in their breast post low risk DCIS diagnosis and over what timescale. The published evidence (6) suggests that the current interruption of women's lives for urgent and often major surgical 'cancer' treatment within 31 days of diagnosis of low risk DCIS is unnecessary, inappropriate and misleading for the recipient. This urgent

Page 1 of 48 Version 4.0, 15th March 2016

treatment must be a contributing factor to the patient's perception of the risk of dying from their disease being similar to that of patients with invasive disease (9).

The Benefits and Harms of Breast Screening; An Independent Review was commissioned by the Department of Health to address these issues of debate and was published in full in 2013 (10). They found benefits and harms of the programme and importantly established that screening saves lives but also that over diagnosis exists. The panel estimated that for 10,000 UK women invited to screening from age 50 for 20 years, about 681 cancers will be found, of which 129 will represent overdiagnosis, and 43 deaths from breast cancer will be prevented. In round terms therefore, for each breast cancer death prevented, about three overdiagnosed cases will be identified and treated.

The panel's review of overdiagnosis lead to their recommendation for further research into DCIS, in particular this proposed study to examine the need for treatment of low grade DCIS.

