2.2.2 Outcome Measures of Main Trial

2.2.2.1 Primary Outcome

Ipsilateral invasive breast cancer free survival time: defined in whole days measured as time from randomisation until first report of ipsilateral invasive breast cancer or death (from any cause), whichever happens first. Patients who withdraw or who are lost to follow-up will be censored at the date last known to be alive and free of disease. Patients not having an event at the time of analysis will be censored at the date last seen alive and free of disease.

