2.2.2.2 Secondary Outcomes

- Time to development of ipsilateral invasive breast cancer: defined in whole days measured as time from randomisation until first report of ipsilateral invasive disease. Randomised patients with no evidence of disease will be censored at the last reported follow-up
- Time to development of any invasive breast cancer: defined in whole days measured as time from randomisation until first report of any invasive disease. Randomised patients with no evidence of disease will be censored at the last reported follow-up
- Time to development of contralateral invasive breast cancer: defined in whole days measured as time from randomisation until first report of contralateral invasive disease. Randomised patients with no evidence of disease will be censored at the last reported follow-up
- Overall survival time: defined in whole days measured as time from randomisation to date of death from any cause. Patients who withdraw or who are lost to follow-up will be censored at the date last known to be alive. Patients who remain alive during the course of the study will be censored at the date last seen alive
- Time to mastectomy: defined in whole days measured as the time from randomisation until time of mastectomy surgery. All other patients will be censored at last know follow-up assessment having not had a mastectomy

Page **7** of **48** Version 4.0, 15th March 2016

- Time to surgery: defined as time in whole days measured from randomisation until first reported ipsilateral breast cancer/DCIS related surgery. All other patients will be censored at last known follow-up assessment having not received surgery
- Quality of Life: will be assessed using the following:

Brief COPE

Spielberger State-Trait Anxiety Inventory

SF-36v2 Health Survey

Euro Qol EQ-5D

- Quality-adjusted Life years (QALY): survival time and longitudinal measures of EQ-5D will be combined to form a QALY outcome
- Costs and cost-utility: per-patient costs will be calculated from Patient Costs Questionnaires and
 utilising clinical data and key resource use data from Case Report Forms (CRFs), enabling economic
 evaluation of clinically important outcomes such as cost per additional surgical treatment avoided and
 cost per diagnosis of ipsilateral breast cancer and cost per QALY

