4.1 Inclusion Criteria

- 1) Female, aged ≥ 46 years
- 2) Screen-detected or incidental microcalcification
- 3) Histologically confirmed diagnosis of non-high grade DCIS confirmed by local pathologist (for both breasts if bilateral disease) by:

Small volume core biopsy and Vacuum Assisted Core Biopsy (VACB)

Or

Vacuum Assisted Core Biopsy (VACB) alone as first line diagnostic approach

Or

Small volume biopsy or VACB plus open diagnostic surgical biopsy (without clear margins)

Or

Page 8 of 48 Version 4.0, 15th March 2016

Open diagnostic surgical biopsy (without clear margins)

(in accordance with the current NHSBSP Guidelines for Pathology Reporting in Breast Cancer Screening)

- 4) DCIS diagnosed ≤90 days before registration
- 5) Bilateral DCIS is permitted if non-high grade DCIS is confirmed in both breasts at the time of mammogram and diagnostic biopsy
- 6) Able to give informed consent and comply with the trial schedule and completion of Patient Reported Outcome questionnaires
- 7) Patient fit and willing to undergo surgery
- 8) Written informed consent obtained

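### Five secondary time-to-event outcomes censor women who die without the event and are shown by Kaplan-Meier, so absolute risks read from the curves are at or above the proportion actually affected

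*Protocol*

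**What the plan says.** The primary outcome (Protocol 2.2.2.1) counts death as an event. It runs to "first report of ipsilateral invasive breast cancer or death (from any cause), whichever happens first".

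The secondary outcomes (2.2.2.2) are built differently. For each of the three time-to-invasive-cancer outcomes the rule is: "Randomised patients with no evidence of disease will be censored at the last reported follow-up". For mastectomy it is: "All other patients will be censored at last know follow-up assessment having not had a mastectomy". For surgery it is: "All other patients will be censored at last known follow-up assessment having not received surgery". None of the five names death. A woman who dies without the event fits no other category, so she is censored. This follows by implication; no sentence states it.

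Section 16.2.2 then sets one method for everything: "Time to event outcomes will be calculated for all patients and methods described by Kaplan and Meier used to present survival curves", followed by "The log-rank statistic will be used to test hypotheses". The protocol mentions no competing-event method.

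On intended use, section 1.1.1 says: "Women will be able to make appropriate choices based on the chances of invasive disease developing in their breast", and adds the timescale. Entry is open to "Female, aged ≥ 46 years" with no upper limit. Section 16.2.3 plans descriptive analysis by age stratum, the oldest being over 65 (6.2.2). Section 16.2.5 plans further analysis after at least five more years of mammographic follow-up.

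**The concern.** Kaplan-Meier treats a censored woman as still able to have the event later. That suits loss to follow-up but not death. With deaths censored, one minus Kaplan-Meier estimates the risk in a setting where death does not remove women from risk. It does not estimate the share of women who will actually have the event.

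The rationale wants the trial to tell women how likely invasive disease is, and when. The primary outcome cannot give that figure alone because it mixes cancer with deaths from any cause. The secondary cancer outcomes are the ones that isolate it, and they are the ones affected. What is at stake is the accuracy of the absolute risks reported, mainly at 10 years and where mortality is higher. No planned test is at stake.

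**Working it through.** **The plan's own figures.** The protocol states no risk for these secondary outcomes, so there is none to reproduce. Its primary sizing does reproduce. With a hazard ratio of 2.02, one-sided 5%, 80% power and 1:1 allocation, the Schoenfeld formula gives 4 × (1.645 + 0.842)² / (ln 2.02)² = 50.0 events. With exponential survival at five-year rates of 2.5% and 5%, 6 years of uniform accrual and at least 5 years of follow-up, the average event probability is 5.92%. That gives 50 / 0.0592, or 846 patients using the unrounded probability. Allowing 10% gives 931 (× 1.1) or 940 (÷ 0.9), against the stated 932. Nothing below alters these numbers.

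**Inputs from the protocol.** The five-year ipsilateral invasive cancer rate is 2.5% in the Surgery arm (16.2.6). The rate at the margin is 5%, from a 95% cancer-free rate (16.2.6).

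**Assumptions.** Hazards are constant. Ten-year mortality is taken as 5%, 10%, 15% and 25%, because the protocol gives no age-specific mortality. Its only overall figure is 11% in a cited DCIS trial (1.1.5), with no length of follow-up stated.

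**Formulas.** With cancer hazard h and death hazard m:

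- One minus Kaplan-Meier, deaths censored: 1 − exp(−h t)
- Cumulative incidence, death competing: h/(h+m) × [1 − exp(−(h+m) t)]

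The second cannot exceed the first, since each increment of cancer risk is also multiplied by the probability of being alive. They are equal if no death precedes an event.

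**Numbers at the 5% rate.** h = −ln(0.95)/5 = 0.01026 per year and m = −ln(1 − 10-year mortality)/10. One minus Kaplan-Meier is 5.00% at 5 years and 9.75% at 10 years in every row.

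| Assumed 10-year mortality | Cumulative incidence, 5 years | Excess (points) | Cumulative incidence, 10 years | Excess (points) |
|---|---|---|---|---|
| 5% | 4.94% | 0.06 | 9.51% | 0.24 |
| 10% | 4.87% | 0.13 | 9.26% | 0.49 |
| 15% | 4.80% | 0.20 | 9.01% | 0.74 |
| 25% | 4.66% | 0.34 | 8.49% | 1.26 |

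In relative terms the 10-year figure is about 3% to 15% too high.

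**Numbers at the 2.5% rate.** h = 0.00506 per year. One minus Kaplan-Meier is 2.50% and 4.94%. Over the same mortality range the excess is 0.03 to 0.17 points at 5 years and 0.12 to 0.64 points at 10 years, about half the values above.

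**Reading the cited 11% as a 10-year figure (assumption).** At the 5% rate the excess is 0.14 points at 5 years (5.00% against 4.86%) and 0.54 at 10 years (9.75% against 9.21%).

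**Mastectomy.** Surgery is expected within 60 days of randomisation (7.1.2.1). If 30% of the Surgery arm have mastectomy in that window (the current-practice share in 1.1.1), the two estimates are 30.0% and 29.97% at 11% ten-year mortality. In Active Monitoring, an assumed 20% at 10 years becomes 18.9% at the same mortality. For this outcome any distortion falls almost wholly on the Active Monitoring arm.

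**The case against.** The strongest reply is that this is one generic sentence about presenting curves. It does not say that one minus Kaplan-Meier will be reported as the proportion of women affected, and an analysis plan that is not shown may handle competing deaths. The statement about women's choices is background and names no estimator. A curve with deaths censored is also a legitimate description of the cause-specific process.

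Part of this stands. The censoring of deaths is implied, and the link to patient choice is the rationale's, not the analysis section's. But the protocol is not silent: it names a method and applies it to every time-to-event outcome without exception. An analysis plan using cumulative incidence would have to depart from that text.

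The second reply is size, and it stands. With about 466 women per arm (932/2) and a simple binomial standard error ignoring dropout, the 95% half-width is about ±2.0 points at a 5% risk and ±2.7 points at 9.75%. Both exceed the bias computed here. The bias is nevertheless systematic and does not shrink with more data. The higher mortality values may also be unrepresentative, since entry requires fitness for surgery (4.1) and excludes serious or unstable conditions that would prevent compliance (4.2).

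A reader might infer more than the documents support:

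- That the curve always exceeds the true proportion. It is at or above it.
- That the error matters most in women over 65 because the choice between surgery and monitoring is closest there. No section says so. Only the mechanical point holds: the gap widens as mortality rises.
- That the test is invalid. The log-rank test remains valid for comparing cause-specific hazards.

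**Conclusion.** The point holds as a minor one. Followed as written, the protocol yields absolute risks for five secondary outcomes that are at or above the true proportion of women affected. The direction is certain. The size rests on constant hazards and assumed mortality: over 5% to 25% ten-year mortality the excess is a few tenths of a point or less at 5 years and at most about 1.3 points at 10 years, for cancer rates in the protocol's planning range.

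It would be tempting to read this as a threat to the non-inferiority conclusion, but the documents do not support that. The primary outcome and overall survival count death as an event, so Kaplan-Meier is right for both, and the 50 events and 932 patients do not depend on it.

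**What to change.** In section 2.2.2.2, state that death without the event is a competing event for time to ipsilateral, any and contralateral invasive cancer, time to mastectomy and time to surgery. In section 16.2.2, limit Kaplan-Meier to the primary outcome and overall survival. For the five outcomes, present Aalen-Johansen cumulative incidence by arm, with confidence intervals at 5 and 10 years, and descriptively by age stratum in line with section 16.2.3. Keep the log-rank test for comparison, described as a comparison of cause-specific hazards.

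No new data are needed, because the Death Form already records the date of death (13.1). The downside is slightly more analysis and reporting work: a second estimator alongside Kaplan-Meier and some additional descriptive tables.
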